Penetrating abdominal injury	An injury penetrating the peritoneum into the abdominal cavity
Peritonitis	Rigid involuntary general tenderness of the abdominal wall.
Postoperative complication	Any deviation from the ideal postoperative course that is not inherent in the procedure and does not comprise a failure to cure. Classification of Surgical complications will be done according to Clavien-Dindo (appendix 2).
SSI	Surgical Site Infection is present when one of the following criteria are met: i. Purulent discharge from surgical site ii. Positive culture iii. Surgical site requires reopening iv. SSI is present as judged by attending physician Severity according WHO guidelines (appendix 3).

Background

Trail location

In 2014, Islamic State Group (ISg) made significant territorial gains in several governorates in Iraq and captured key cities, including Fallujah and Mosul¹. ISg is unique among terrorist groups in that it employs a combination of conventional maneuverer warfare with tactics such as human shields, improvised explosive devices (IED's), suicide bombers and drones in order to capture and hold territory. These tactics are indiscriminate, leading to excessive civilian casualties².

Emergency Hospital (EH) is one of two trauma hospitals in Erbil, a major metropolitan area in Kurdistan Region of Iraq. Erbil is located 94 kilometres east of the city of Mosul. Mosul is the provisional capital of the Nineveh region of Iraq. In mid-October 2016, the offensive to liberate Mosul from the ISg was initiated. EH was assigned by the Governate to exclusively provide care to injured from the armed conflict in and around Mosul. Since late December 2016 treatment facilities, run by other emergency care providers, have opened closer to Mosul. EH since then mainly served as a referral hospital.

The battle of Mosul formally ended on 10 July, 2017. The admission of casualties from Mosul to EH has since then diminished significantly. NGOs and other emergency care providers have also decreased their activities since.

Previous reports on exploratory laparotomy in conflict settings

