Outcome of exploratory laparotomy (ex-lap) following war-related injuries has previously been extensively studied and reported on³⁻⁷. These reports have mainly concentrated on causes for and findings at ex-lap, and postoperative mortality (table 1). Few studies have focused on the differences in injury mechanism, complexity of injuries and outcome between civilians and combatants, especially in urban conflicts where IED's, human shields and suicide bombers are used².

Table 1. Findings at ex-lap and postoperative mortality in different conflicts

Conflict	Nb. of Ex-laps	Negative explorations	Small intestinal injuries	Colon injuries incl. rectum	Other injuries	Postoperative mortality
Chad,1980³	210	4,8%	33,0%	21,1%	32,7%	22,5%
Lebanon 1975-85⁴	1314	9,7%	24,7%	21,2%	55,0%	9,5%
Former Yugoslavia 1991-95⁵	93	4,3%	30,0%	28,4%	41,5%	10,8%
Gaza 2000-03⁶	230	6,5%	26,7%	17,9%	55,3%	7,4%
Mosul, Iraq, 2006⁷	153	15%	23,7%	18,7%	57,6%	33,3%

Justification

There is a need for better understanding of demographics and outcome of ex-lap following abdominal injuries sustained in urban conflicts where IEDs, human shields and suicide bombers are used. The use of these indiscriminate weapons could affect civilians to a greater extent than combatants⁸. We therefore hypothesize that the use of indiscriminate weapons in an urban setting causes more extensive abdominal injuries to the civilian population than to combatants. The knowledge gained from this study could be crucial when planning surgical staffing and facility needs in similar contexts.

Potential Risks and Benefits

Since this is an observational retrospective cohort study without any interventional methods it poses little to no harm for the participants. A potential benefit for future patients would be an increase in understanding among health care providers regarding what kind of abdominal injuries indiscriminate weapons cause. Furthermore, a better understanding of what impact the use of indiscriminate weapons has on the civilian population.

Aim of Study

To assess whether civilians have more complex abdominal injuries than combatants in an urban battle characterized by the use of indiscriminate weapons.

Primary Measure

Differences in injury mechanism, organs injured, surgical treatment given, postoperative complications and outcome between civilians *and* combatants.

Secondary Measures

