Data was routinely prospectively collected on paper based patient forms in the clinical setting at EH. A *patient database* with consecutive patients treated between October 17, 2016 and July 31, 2017 was created. It is expected that the database will contain a total of 1,800 patients to produce approximately 160 evaluable subjects. Paper based *patient files* will be queried for demographic information, combatant or civilian status, admission dates, discharge dates, whether the injury was conflict-related or not, geographical site for injury, cause and mechanism of injury, prehospital data, medical history, vital signs at hospital admission, anatomical data and details regarding extent of abdominal injury, number and type of surgeries, details on surgery, need for ICU care, in hospital complications, re-admission including cause of re-admission, outcome including death and cause of death. Paper based data will be entered into a computer database using Epidata entry software (The Epidata Association, Odense, Denmark).

Patient Files

- Time of admission (specified)
- Age in years (specified)
- Sex (Male/Female/Unknown)
- Ethnicity (Arabic/Kurdish/Other/Unknown)
- Civilian/Combatant (Iraqi/Peshmerga/ISg/Unknown/Other)
- Time of injury (specified)
- Geographical location where injury occurred (specified)
- War-related injury (Yes/No/Unknown)
- Cause of injury (Bullet/Shell/Mie/IED/Unknown/Other)
- Mechanism of injury (Gunshot/Stab/Blast/Crush/Fragment/Burn/Traffic accident/Unknown/Other)
- Care prior to admission to EH (First Aid/Medical/Surgery/None given/Unknown)
- Provider of care prior to EH (MSF/Aspen/ICRC/Samaritan Purse/DoH/None)
- Mode of transport to EH (Military/Private car/Motorcycle/Ambulance/Unknown)
- Medical history (Healthy/Prior surgery/ Prior medical/Unknown)
- Body temperature (specified in Celsius)
- Heart rate (specified in beats/min)
- Blood pressure (specified in systole/diastole mmHg)
- Pregnant (Yes/No/Unknown)
- Pregnancy status based on (Lab/Question/Status/Unknown)
- Site and extent of abdominal wound (specified)
- Other injuries (Yes/No/Unknown, specified)
- Preoperative haemoglobin (specified in g/dL)
- Preoperative transfusions (Yes/No/Unknown, specified)
- Use of preoperative radiology (Yes/No/Unknown, specified)
- Time and date of procedure (specified)
- Duration of procedure (specified in hours and minute)

- Antibiotics prophylaxis (Yes/No/Unknown, specified)
- Procedure done (appendix 1 for definition of findings)

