- Perioperative complication (Yes/No/Unknown, specified)
- Postoperative antibiotic prophylaxis (Yes/No/Unknown, specified)
- Postoperative infection (Yes/No/Unknown, appendix 3 for definition)
- Other postoperative complication (Yes/No/Unknown, appendix 2 for definition)
- Need of postoperative intensive care (Yes/No/Unknown, specified)
- Postoperative transfusions (Yes/No/Unknown, specified)
- Use of postoperative radiology (Yes/No/Unknown, specified)
- Further surgery done (Yes/No/Unknown, specified)
- Discharge (Yes/No/Unknown, specified)
- Follow-up scheduled (Yes/No/Unknown, specified)
- Re-admission (Yes/No/Unknown, specified)
- Deceased during hospital stay (Yes/No/Unknown, specified)
- Remarks

Statistical Analyses

Sample Size

Due to the nature of the study, the sample size will be a convenience sample of the available cases during the study period. It is expected that approximately 160 subjects will be enrolled.

Statistical Methods

Analysis will be done by as treated. A 5% significance level will be used. The difference in dichotomous, such as postoperative complication (primary outcome), and categorical outcomes with more than two categories will be tested using chi-square or Fisher test. For differences in continuous variables t-test will be used. In order to adjust our analysis for possible confounders and effect modifiers we will then use linear, logistic, ordinal or multinomial regression models, according to the nature of the outcome (continuous, binary, ordinal or nominal) with injury mechanism as the dependent variable and civilian/combatant as the main explanatory variable. Important demographic and injury specific parameters such as geographical location, date, age, sex, and injured organs, will then be included in the model as potential confounders.

Safety and Monitoring

Participant Confidentiality

The use of identification numbers will ensure anonymity in the data analysis. The participant's age, gender and demographic characteristics will be used as identifying features for analysis. The research team will ensure the ethical principles of beneficence, non-maleficence, justice and respect of patients are adhered to throughout the study.

Data Collection and Management

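### Complications, intensive care, transfusion and death reflect the whole injury load, but extra-abdominal injury, which the CRF collects, is not a pre-specified covariate, so a group difference may be misread as abdominal severity

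*Combined protocol and SAP*

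**What the plan says.** - **Aim and hypothesis.** Aim of Study: "To assess whether civilians have more complex abdominal injuries than combatants". Justification: the weapon type "causes more extensive abdominal injuries to the civilian population than to combatants". Both concern the abdomen.
- **Comparisons.** Primary Measure lists injury mechanism together with "organs injured, surgical treatment given, postoperative complications and outcome between civilians" and combatants.
- **Primary outcome and test.** Statistical Methods: "The difference in dichotomous, such as postoperative complication (primary outcome), and categorical outcomes with more than two categories will be tested using chi-square" or Fisher's test.
- **Scope of the outcomes.** The List of Definitions describes a complication as "Any deviation from the ideal postoperative course that is not inherent in the procedure", with no limit to the abdomen. In Appendix 2, transfusion falls under Grade II, life-threatening events needing intensive care under Grade IV, and death under Grade V. Death is recorded as "Deceased during hospital stay (Yes/No/Unknown, specified"). The cause is also recorded, but the outcome is not restricted to abdominal causes.
- **Adjustment.** "Important demographic and injury specific parameters such as geographical location, date, age, sex, and injured organs, will then be included in the model" as possible confounders. The sentence before it makes injury mechanism the dependent variable.
- **Data held.** Patient Files lists "Other injuries (Yes/No/Unknown, specified"). CRF item 21 takes a free-text size and depth for up to three such wounds, with any further ones under remarks.
- **Eligibility.** Patients with wounds elsewhere are neither excluded nor stratified.

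**The concern.** The hypothesis is about one body region, but several of the outcomes compared under it belong to the whole patient. A chest, head or limb wound can lead to transfusion, intensive care, a complication or death whatever the state of the abdomen. If one group carries more of these wounds, its outcomes will be worse for a reason unrelated to abdominal severity.

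The misreading is a natural one because Appendix 1 itself ties abdominal severity to complications, with a sharp rise in their rate above a PATI of 25. The variable needed to separate the two explanations is collected, but nothing commits the analysts to use it. No whole-body severity score, isolated-abdominal analysis or with-and-without comparison is planned. An open covariate list leaves the choice until after the data have been seen.

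**Working it through.** **Plan figure.** There is none to reproduce. The only number is about 160 subjects, a convenience sample with no event rate, effect size or group split. All inputs below are therefore assumptions, apart from the 160, the 5% level (taken as two-sided) and the Table 1 mortality range.

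**Formula.** Suppose the two groups have identical abdominal injury. Let p0 be the complication risk without extra-abdominal injury and p1 the risk with it, where odds(p1) = OR × odds(p0). Let c and m be the prevalence of extra-abdominal injury in civilians and combatants. Each group's risk is prevalence × p1 + (1 − prevalence) × p0, so the distortion is (c − m) × (p1 − p0).

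**Worked case.** With p0 = 0.30 and OR = 3, odds(p1) = 0.4286 × 3 = 1.286 and p1 = 0.5625. With c = 0.70 and m = 0.40:
- civilians: 0.70 × 0.5625 + 0.30 × 0.30 = 0.484
- combatants: 0.40 × 0.5625 + 0.60 × 0.30 = 0.405
- difference 7.9 points; odds ratio (0.484/0.516)/(0.405/0.595) = 1.38

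**Range.**

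| p0 | OR | c v m | Difference (points) | Group odds ratio |
|---|---|---|---|---|
| 0.20 | 1.5 | 50% v 40% | 0.7 | 1.04 |
| 0.30 | 2 | 60% v 40% | 3.2 | 1.15 |
| 0.30 | 3 | 60% v 40% | 5.3 | 1.24 |
| 0.40 | 3 | 70% v 40% | 8.0 | 1.38 |
| 0.30 | 3 | 40% v 60% | −5.3 | 0.81 |
| any | any | equal | 0 | 1.00 |

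With the gap reversed (40% v 60%), the group odds ratio over the whole grid is 0.81 to 0.92.

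**Second illustration, including death.** Assume major extra-abdominal injury in 50% to 60% of civilians and 30% of combatants.
- Complication risk 60% with and 35% without: 47.5% to 50.0% v 42.5%, a gap of 5.0 to 7.5 points (odds ratio 1.22 to 1.35).
- Death risk 25% with and 8% without: 16.5% to 18.2% v 13.1%, a gap of 3.4 to 5.1 points (odds ratio 1.31 to 1.48).

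**Simulation.** There were 2,000 runs per scenario with p0 = 0.30, no true group effect, and splits of 80/80 and 50/110. Prevalence was 60% v 40% (OR 2 or 3) or 70% v 40% (OR 3). The unadjusted chi-square test rejected in 6.8% to 17.4% of runs, with a median odds ratio of 1.16 to 1.39. Adding the indicator to a logistic model brought rejection to 4.6% to 5.6% and the median odds ratio to 0.98 to 1.00. With 40% prevalence in both groups, both analyses gave odds ratios of 1.00 to 1.01 and rejection of 4.8% to 5.7%.

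**Context.** At 160 subjects and baseline risks of 20% to 50%, the difference detectable with 80% power is about 20 to 22 points for an 80/80 split and 21 to 24 for 50/110. Table 1 mortality runs from 7.4% to 33.3%, so 160 × 0.074 = 11.8 and 160 × 0.333 = 53.3, or about 12 to 53 deaths. With a 50/110 split and prevalence of 60% v 40%, the isolated-abdominal subset is 50 × 0.4 = 20 civilians and 110 × 0.6 = 66 combatants.

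**The case against.** - **The covariate list only gives examples.** This stands. Extra-abdominal injury could still be added, and injured organs is not defined as abdominal organs only. The accurate charge is that the variable is not pre-specified.
- **The abdomen is measured directly.** This stands in large part. Organs injured is a separate planned comparison, and none of PATI's 14 categories is a limb, chest or head region. If organs injured were similar and complications differed, the tables would show it. However, Statistical Methods does not mention PATI, and its only outcome labelled primary is complication.
- **The imbalance is unknown.** This stands. The documents do not say which group has more wounds elsewhere, or that blast casualties do. The bias may run either way or be absent. That is a reason to tabulate item 21 by group.
- **Other wounds may be part of the weapon effect.** This stands. They come from the same event, and the stated use is planning staff and facilities, for which total burden matters. The unadjusted contrast is therefore not an error. It answers a different question, so both results are needed.
- **The data are thin.** This stands in part. Item 21 has no severity scale, so a none/minor/major grade would be a retrospective judgement on free text. At the low end a death model could hardly carry the named covariates plus one more.

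**Conclusion.** The point holds in a limited form. Whole-patient outcomes are compared under an abdominal hypothesis, and a collected variable that would help to interpret them is not pre-specified. If prevalence differs between the groups, the distortion is about 1 to 8 percentage points over the assumed range, with sign unknown, and false rejection rises to roughly 7% to 17% in the simulated imbalances. With equal prevalence there is none. These sizes rest wholly on assumed risks, prevalences and group splits, and they are well below the 20 to 24 points that the study could detect with 80% power.

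A reader might infer that the plan ignores extra-abdominal injury, that a group with more limb, chest or head wounds will appear to have worse abdominal trauma, or that the plan cannot tell the two explanations apart. The documents do not support this. The covariate list is open, organs injured is compared in its own right, nothing states that complications or death will be read as abdominal severity, and no imbalance is documented.

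**What to change.** 1. Pre-specify an extra-abdominal injury variable from CRF item 21, as any/none or by body region. State how unknown entries are handled, and tabulate the variable by civilian/combatant status.
2. Correct Statistical Methods so that complications, intensive care and transfusion are dependent variables of the regression models. With injury mechanism as the named dependent variable, no adjusted model for these outcomes is clearly specified, and a new covariate would have nowhere to go.
3. For each of these outcomes, report the civilian/combatant contrast with and without the variable, labelled as total and abdominal-attributable burden, with the other covariates unchanged. State whether injured organs is in these models, because adjusting for it removes part of the abdominal burden itself.
4. Do the same for death only if the number of events allows. Report patients with isolated abdominal injury descriptively.
5. Do not add the variable to the comparisons of mechanism, organs injured or PATI. Base the conclusion on abdominal severity on organs injured and PATI, and name PATI in Statistical Methods.

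**Cost.** SAP wording and one variable derived from data already collected. The downsides are one more model term (more if coded by body region), a small descriptive subset, and residual confounding because item 21 has no severity grade.

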Comparison of surgical treatment given, postoperative complications and outcome between patients with prior surgical treatment of their injury *and* patients without prior surgical treatment.

Differences in surgical treatment given, postoperative complications and outcome between patients who receive surgical treatment less than 24 hours from injury *and* patients who receive surgical treatment more than 24 hours from injury will be analysed.

See chapter Data, *patient files*, for detailed primary and secondary measurements.

Investigation Plan

Study Design

A cohort study with retrospective longitudinal data collection using routinely collected clinical data.

Study Period

Consecutive patients presenting at EH between October 17, 2016 and July 16, 2017 that meet eligibility criteria will be included. Patient history information preceding hospital admission will be included.

Study Location

Emergency Hospital, Erbil, Kurdistan Region, Iraq.

Study Duration for Participants

Participants will be followed from admission until discharged from EH.

Study Population

Recruitment Methods

Patients will be included from the surgical ledger at the Surgical Department of EH.

Inclusion Criteria

- All patients treated with ex-lap due to conflict-related penetrating injury presenting at EH between October 17, 2016 and July 31, 2017 will be included.

Exclusion Criteria

- Patients who received treatment several times during the study period will only be counted as one patient.

Information for Patients and Consent

Since this study is based on data from routine care participants will not be informed, nor will consent be asked of participation, as this could introduce bias and confounding factors. There are moreover no risks or potential gains involved for participants. No incentives or inducements will be provided to any participant or staff involved.

Data

Data Sources

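### Prior surgery for the injury and prior medical condition are collected but not named as adjusters in the civilian/combatant comparison of treatment, complications and outcome

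*Combined protocol and SAP*

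**What the plan says.** All references are to the combined protocol and SAP.

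- **Statistical Methods** describes the adjusters as demographic and injury-related and gives five examples: "parameters such as geographical location, date, age, sex, and injured organs, will then be included in the model as potential confounders".
- **Patient Files** (under Data) lists two further items recorded for every patient: "Care prior to admission to EH (First Aid/Medical/Surgery/None given/Unknown") and "Medical history (Healthy/Prior surgery/ Prior medical/Unknown"). They are items 11 and 14 of the Case Report Form (Appendix 4). Item 11 also asks for the procedure and its date.
- **Secondary Measures** makes prior surgery an exposure in its own right: "Comparison of surgical treatment given, postoperative complications and outcome between patients with prior surgical treatment of their injury" and patients without it.
- **Background** says of the period after late December 2016: "EH since then mainly served as a referral hospital".
- **Statistical Methods** identifies the outcome "such as postoperative complication (primary outcome"), but describes the regression as fitted "with injury mechanism as the dependent variable and civilian/combatant as the main explanatory variable".

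**The concern.** The primary comparison sets civilians against combatants on, among other things, surgical treatment, complications and outcome. The first secondary comparison uses those same three measures to contrast patients with and without an earlier operation. The plan therefore regards prior surgery as worth studying in relation to these outcomes, but pools both kinds of patient in the primary comparison and does not name prior surgery as an adjuster.

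At a hospital that took mainly referrals for most of the study period, the share of patients already operated on could be substantial and could differ by status. Medical history raises a similar question: the List of Definitions places men from 50 upwards among civilians, where chronic illness may be commoner.

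At stake is interpretation. The study's hypothesis is that indiscriminate weapons cause more extensive injury to civilians. A difference in complications that came from the route of care or from pre-existing illness could be read as support for that hypothesis, or could hide a real difference.

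**Working it through.** **No figure to reproduce.** The sample of about 160 is a convenience sample. The documents give no complication rate, share with prior surgery, group split or power calculation. What follows is illustration under stated assumptions.

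**Which variables, and when they arise.**

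| Variable | Collected | Named adjuster | Position relative to status |
|---|---|---|---|
| Prior medical condition (item 14) | yes | no | before the injury: candidate confounder |
| Surgery for this injury before EH (item 11) | yes | no | after the injury: possible mediator |
| Date | yes | yes | may track the move to referral work, but not whether a given patient had been operated on |
| Age | yes | yes | partial stand-in for chronic illness; age and sex also largely define status |

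**Size of a crude difference.** Suppose status has no effect on complications except through prior surgery. With shares a and b of prior surgery in the two groups, and complication risks p0 without and p1 with prior surgery,

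crude difference = (b − a) × (p1 − p0).

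| a v b | p0 v p1 | Crude difference |
|---|---|---|
| 30% v 60% | 30% v 20% | 0.30 × (−0.10) = −3 points |
| 30% v 40% | 30% v 30% | 0.10 × 0 = 0 |
| 30% v 40% | 30% v 50% | 0.10 × 0.20 = +2 points |
| 40% v 55% | 35% v 55% | 0.15 × 0.20 = +3 points |
| 30% v 50% | 30% v 50% | 0.20 × 0.20 = +4 points |
| 30% v 55% | 35% v 60% | 0.25 × 0.25 = +6.25 points |
| 30% v 60% | 30% v 60% | 0.30 × 0.30 = +9 points |
| 20% v 60% | 30% v 65% | 0.40 × 0.35 = +14 points |

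The same formula for chronic illness, assuming 15% v 3% affected and complication risks of 70% with and 40% without it, gives 0.12 × 0.30 = 3.6 points before any adjustment for age.

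**Scale.** With 80 patients per group and a two-sided 5% test, 80% power needs a true difference of about 20 to 22 points at baseline rates of 20% to 40%. All the differences above are smaller than that. In the 80 v 80 normal approximation, the chance that the crude test is significant is about 5% at 0 points, 8% at +4, 21% at +9 and 43% at +14.

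**Room in the model.** At assumed complication rates of 20% to 40%, 160 patients give 0.20 × 160 = 32 to 0.40 × 160 = 64 events. With 8 parameters that is 32/8 = 4 to 64/8 = 8 events each. If the 14 PATI organs entered separately, a model of about 18 to 20 parameters would have 32/20 = 1.6 to 64/18 = 3.6 events each.

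**The case against.** **The list is open.** It is introduced with the words such as, so nothing is excluded. That is true, and a reader who infers that the plan rules these two variables out would be wrong. But neither fits plainly under demographic or injury-related parameters, and the plan already uses one of them as an exposure. They should be named.

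**Prior surgery is not a clean confounder.** It precedes EH care, but it follows the injury and therefore civilian/combatant status. If status affects access to first care, prior surgery is part of how status acts, and adjusting for it answers a different question. This stands, and it determines the form of the fix. Medical history precedes the injury and does not have this difficulty.

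**The direction is unsupported.** A reader might infer that the group referred more often after an earlier operation will appear to have more complications. The documents do not support that. They do not say which group was referred more, or that prior surgery raises risk. Patients who reached EH after a first operation had survived both it and the transfer, so the sign could reverse.

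**The rejection rates are not those of the planned analysis.** A reader might take 21% or 43% as its false-positive rate. Those figures come from assumed inputs and a crude test. The plan goes on to adjust for date, location, age, sex and injured organs, which may remove part of the difference. If prior surgery is a mediator, a difference arising through it is not a false positive for the total effect of status.

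**The regression wording names another outcome.** Read literally, the dependent variable is injury mechanism, and surgery after the injury cannot confound that model. This stands: the point applies only to models of treatment, complications and outcome.

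**Conclusion.** The point holds as a gap in the named adjustment set: two collected variables with a plausible bearing on complications are not named, and date and age only partly stand in for them. It does not establish that the planned comparison is biased. That would require an imbalance by status and an association with complications, and the documents report neither.

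The range of about −3 to +14 points depends wholly on the assumed shares and risks. It describes the crude comparison, not what would remain after the planned adjustment. This is a cheap improvement, not a flaw that invalidates the analysis.

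**What to change.** In Statistical Methods:

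1. Reconcile the sentence that makes injury mechanism the dependent variable with the stated primary outcome, and say which models are fitted to which outcomes.
2. In the models for surgical treatment, complications and outcome, add prior medical condition (yes/no, item 14) as a covariate.
3. Report the civilian/combatant estimate without and with surgery for this injury before EH (yes/no, item 11). Label the second a sensitivity analysis, because prior surgery may be a mediator.
4. Keep item-11 surgery distinct from the prior-surgery category of item 14, which is medical history.
5. State how unknown values of either item are handled, and report their number by group.

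The cost is a few sentences and no new data. One or two degrees of freedom are used where only about 32 to 64 events may be available, so the other covariates should be kept sparing, for example by summarising injured organs in one score. Some patients will have unknown values.
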